- Severe Depression and/or perceived risk to self or others (mental health resources will be provided and if suicide risk, approved suicide protocol will be utilized);
- Currently receiving active behavioral therapy for anger.
- On drug research study for irritability, anger, aggression

Note: Participants will not be excluded if they do not have caregiver.

Sample Size Calculation. Forty participants (20 per group) will be enrolled to allow for 20% dropout. Thirty-two participants (16 per group) are expected to finish the study. For Aim 1, feasibility and satisfaction percentages of 80%, a sample size of 30 will allow these proportions to be estimated to within 13% using one-sided 95% confidence intervals. For between group effect sizes for Aims 2 and 3, a sample size of 21 per group will detect an effect size of 0.9 standard deviations with 80% power using a two-sided t-test at a .05 level of significance. An ANCOVA model with pre/post correlation of 0.5 can reduce the sample size needed by 25% or to 16 per group. For within group effect sizes for Aims 2 and 3, 16 subjects will provide 80% power to detect a difference in means of .78 standard deviations using a two-sided paired t-test at the .05 level of significance.

Recruitment. The Rehabilitation Hospital of Indiana (RHI), an affiliate of Indiana University (where the PI and Co-I's have offices), will be a primary source of recruitment (see [name] LOS). IU/RHI is one of 16 nationally recognized Traumatic Brain Injury Model Systems (TBIMS) sites in the United States, making it a strong site for recruitment of this population. On average, RHI admits around 120 individuals with TBI annually; $>1,000$

individuals with TBI are seen in the RHI outpatient clinics. We will use 1) past RHI inpatients, 2) RHI Outpatient Clinic, 3) RHI Research Registry (n=295), and 4) IU/RHI TBIMS Database (>230 enrolled to date). We will recruit through letters sent by physicians to their patients, pre-clinic chart screening, clinician discussions with patients, flyers posted in RHI, recruitment videos shown around the facility, researchmatch.com and through The Rehabilitation Hospital of Indiana's Facebook page. Flyers will be distributed at TBI support groups and the Brain Injury Association of Indiana. RHI patient letters will be followed with a phone call to confirm receipt of the letter and inquire about interest in the study. See Pre-screen below.

Outcome Measures.

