Cognition/ Executive Functioning: We will assess executive functioning skills for attention, dis-inhibition and verbal fluency. The following tests were chosen based on findings from our preliminary study. Color-word interference (Stroop): Attention and dis-inhibition will be assessed with a commonly used color-word interference test that assesses skills such as basic color naming; word reading; and names of colors written in different color ink (participants must name the color of the ink, not read the words). Verbal Fluency: assesses word association fluency; we will examine letter fluency and category fluency. This test measures a person's ability to make verbal associations to letters and categories. Responses for verbal fluency will be audio recorded for data integrity.

Neurobehavioral Functioning: We will evaluate how participants' caregivers perceive the neurobehavioral functioning of our participants with TBI with the Frontal Systems Behavior Scale (FrSBe).^{18,19} It is a 46-item subjective questionnaire that measures apathy, dis-inhibition, and executive dysfunction with a 5-point Likert scale. The FrSBe has good reliability and validity^{18,19} and has been used in variety of clinical populations, including brain injury and Alzheimer's disease.²⁰

Table 1a. ICAN MEASURES AND TIMELINE (Subjects with TBI)

	T0 (screen)	T1	T2	T3 (WLC only)
Consent/ HIPPA*	X			
Demographics*; TBI History*; medication infor and therapy status*	X (inc)			
Med and therapy status update only*		X	X	WLC only
Discourse Comprehension Test*	X (inc)			
Epps stories (attribution and anger to hypothetical scenarios)	X (inc)		X	WLC only
AIHQ Scenarios	X (inc)	X**	X	WLC only
IRI Perspective Taking and Empathetic Concern*	X (inc)	X**	X	WLC only
Buss Perry Aggression*	X (inc)		X	WLC only
NIH Toolbox Anger Affect*		X	X	WLC only
TASIT (theory of mind)		X	X	WLC only
PHQ9 (Depression)*	X (inc)		X	WLC only
GAD7 (anxiety)*		X	X	WLC only
TAS-20 (alexithymia)*		X	X	WLC only
DERS (emotion regulation)*		X	X	WLC only
COWAT verbal fluency (cog f)*	X			
Color word interference (Stroop) (cog f)	X			

Patient Global Impression of Change in Anger and Aggression*			X	WLC only
Patient Global Impression of Change in Empathy/ Perspective Taking*			X	WLC only
Client Satisfaction Questionnaire 8 (CSQ-8)*			ICAN only	WLC only
Post-Treatment Qualitative Interview*			ICAN only	WLC only
RA opinion of group allocation			X	

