Satisfaction Survey (CSQ8): To encourage honest feedback and ensure blinding of RA's, an unblinded RA will be responsible for collecting data on the CSQ-8 within approximately 1-2 weeks of completing the intervention (proximal to Time 2 for ICAN subjects and Time 3 for WLC subjects). In the case of withdrawal from treatment, the CSQ-8 may be conducted upon withdrawal from treatment, if the participant is agreeable. If participants withdraw, reasons for withdraw will attempt to be collected. At the end of the CSQ-8, the participant is presented with an optional comments section regarding their feedback and thoughts about what they liked/ did not like about the program.

Post-Treatment Qualitative Interview: To encourage honest feedback and ensure blinding of RA's, an unblinded RA will be responsible for administering the post-treatment Interview with the participant over the phone, via mail, email or in person within 1-2 weeks of completing treatment (proximal to Time 2 for ICAN subjects and Time 3 for WLC subjects).

Statistical Analysis Plan.

Primary Analyses. For Aim 1, the proportion of participants who complete at least 5 out of 6 sessions, and the proportion of participants who have satisfaction ratings that are average or higher on the standardized CSQ-8 will be calculated. For between group comparisons for Aims 2 and Aim 3, the primary analysis will be ANCOVA models with T2 measures as the outcomes, treatment group as the explanatory variable, and covariates of wave and T1 outcomes (except CaGIC which will not have T1 data since it is only collected at T2). Effect sizes (ω^2) will be calculated.

Secondary Analyses. WLC control outcomes at T2 will be compared to T1 for the ICAN and WLC group. If there are no significant differences, secondary analyses combining the data from the two treatment groups (assessments before and after intervention) will include ANCOVA, paired t-tests, and estimating effect sizes.

Missing Data. We will compare all baseline variables between subjects who drop out of the study to those who don't using two-sample *t* tests, chi-square tests or their non-parametric equivalents as appropriate. Also, we will collect as much information regarding reasons for missing data as possible. If we find that the missing data appear to be not at random, this important information will be used in designing the larger trial. Because of the small sample size, we will not attempt to model the missing data mechanism in this study.

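### The 16-per-group power statement relies on a pre/post correlation that PGIC and CaGIC cannot have, and the SAP's T1 covariate does not match the assessment schedule

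*Combined protocol and SAP*

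**What the plan says.** The Sample Size Calculation treats the between-group comparisons of Aims 2 and 3 together. It starts from a two-sided t-test at the .05 level, aiming for 80% power: "For between group effect sizes for Aims 2 and 3, a sample size of 21 per group will detect an effect size of 0.9" (in SD units). It then takes a saving: "An ANCOVA model with pre/post correlation of 0.5 can reduce the sample size needed by 25% or to 16 per group". That figure equals the planned number of completers: "Thirty-two participants (16 per group) are expected to finish the study".

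Table 1 and the Outcome Measures text make PGIC and CaGIC secondary outcomes in Aim 2 (perspective taking and empathy) and Aim 3 (aggression). In Table 1a the rows "Patient Global Impression of Change in Anger and Aggression" and "Patient Global Impression of Change in Empathy/ Perspective Taking" have no entry at T0 or T1; the first is at T2. Table 1b likewise starts CaGIC at T2. The note under the exclusion criteria allows enrolment without a caregiver.

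The SAP's Primary Analyses specify an ANCOVA of the T2 measure on treatment group, with "covariates of wave and T1 outcomes (except CaGIC which will not have T1 data since it is only collected at T2"). PGIC is not named in that exception.

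Table 1a schedules "Buss Perry Aggression" (the primary outcome) and "Epps stories (attribution and anger to hypothetical scenarios") at T0, with no T1 entry. AIHQ and IRI are collected at T1 only for participants who missed them at T0 because of a protocol change.

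**The concern.** The drop from 21 to 16 per group comes entirely from the correlation between a pre-treatment score and the T2 score. A rating of change has no pre-treatment score, so the saving is not available to it. The stated sensitivity therefore does not hold for four secondary measures (PGIC and CaGIC, in each of two aims), and a null result on any of them could be read as better powered than it was.

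The covariate rule has the same origin. Read literally, it asks for a T1 PGIC value that is never collected. It also asks for T1 values of the AQ and Epps scenarios, which the schedule places at T0, and of AIHQ and IRI, which most participants would have only at T0. These four measures do have a score before randomization, so their power is not in question; the defect there is in the definition of the covariate.

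**Working it through.** **Inputs.** From the Sample Size Calculation: effect d = 0.9 SD, two-sided alpha 0.05, r = 0.5, 20 enrolled and 16 finishing per group. From Procedures: 4 to 7 waves. The documents give no PGIC-specific effect size, no caregiver rate and no wave variance. The plan's own 0.9 SD is used throughout, and ranges are assumed for the other two.

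**Formula.** For n per group, k covariate degrees of freedom, and a fraction R² of outcome variance explained by covariates:

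- noncentrality = d / √(1 − R²) × √(n/2)
- df = 2n − 2 − k
- power = probability that a noncentral t with these values exceeds the two-sided 5% critical value in absolute size

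**Reproducing the plan.**

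- t-test, n = 21: noncentrality 0.9 × √10.5 = 2.916, df = 40, power 0.812. At n = 20 power is 0.792, so 21 is the smallest n reaching 80%.
- ANCOVA saving: 21 × (1 − 0.5²) = 15.75, rounded up to 16.
- ANCOVA, n = 16, R² = 0.25, k = 1: noncentrality 0.9/√0.75 × √8 = 2.939, df = 29, power 0.811.
- Dropout: 16 / 0.8 = 20 enrolled per group.

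The plan's figures are right for an outcome with a pre-treatment score and r = 0.5.

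**PGIC, no baseline covariate.**

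| n per group | noncentrality | df | power at 0.9 SD | effect with 80% power |
|---|---|---|---|---|
| 16 (expected finishers) | 0.9 × √8 = 2.546 | 30 | 0.693 | 1.02 SD |
| 20 (no loss) | 0.9 × √10 = 2.846 | 38 | 0.792 | 0.91 SD |

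**PGIC, adjusting for wave.** The SAP keeps wave in the model. Four waves cost 3 df and seven cost 6 df. Assuming that wave explains 0 to 10% of the variance:

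| n per group | wave R² | power, 4 waves | power, 7 waves |
|---|---|---|---|
| 16 | 0 | 0.689 | 0.685 |
| 16 | 0.03 | 0.703 | 0.699 |
| 16 | 0.10 | 0.735 | 0.731 |
| 20 | 0 | 0.790 | 0.788 |
| 20 | 0.03 | 0.802 | 0.800 |
| 20 | 0.10 | 0.831 | 0.829 |

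To reach 80% at 16 per group, wave would have to explain 23% (4 waves) to 24% (7 waves) of the variance. At 20 per group, 2.4% to 3.0% is enough.

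**CaGIC, no covariate, assumed caregivers per group.**

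| caregivers per group | power at 0.9 SD | effect with 80% power |
|---|---|---|
| 8 | 0.389 | 1.51 SD |
| 10 | 0.478 | 1.32 SD |
| 12 | 0.559 | 1.20 SD |
| 14 | 0.630 | 1.10 SD |
| 16 | 0.693 | 1.02 SD |

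**Covariate rule against the schedule.**

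| Outcome | Pre-randomization visit in Tables 1a and 1b | What the SAP asks for |
|---|---|---|
| PGIC (both items) | none | T1 value |
| CaGIC | none | exempt |
| AQ (primary), Epps | T0 | T1 value |
| AIHQ, IRI | T0; T1 only if missed at T0 | T1 value |
| NIH Toolbox Anger (PROMIS) | T1 | T1 value |

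Of these outcomes, the rule fits the schedule as written only for CaGIC and the anger short form.

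**The case against.** The strongest reply is that nothing stated is miscalculated. The ANCOVA sentence says what such a model can save, which by its own terms presupposes a pre score, and the sentence before it already gives 21 per group without a covariate. The trial is a small feasibility study aimed at effect size estimates, only secondary outcomes are affected, and separate power figures for each are not usually demanded. With no dropout PGIC power is 79%, close to nominal. The SAP already drops the baseline for CaGIC, so leaving out PGIC looks like a slip, and an analyst would have to omit a value that does not exist. For the AQ and Epps scenarios, T0 holds the only scheduled pre-treatment score, so the intended covariate can be inferred.

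Much of this stands as a limit on weight. The gap is one of scope, not a wrong calculation; the primary outcome's power is intact; and the caregiver and wave ranges are assumptions. The CaGIC range also leaves out wave, which the SAP would keep in that model.

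It does not remove the problem. The paragraph covers both aims, names no exception, and arrives at exactly the number expected to finish, so the design depends on the saving. The dropout that takes PGIC from 79% to 69% is the plan's own 20%. A pre-specified covariate should not have to be inferred, least of all for the primary outcome.

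**Conclusion.** The concern holds. For PGIC, the expected 16 per group gives about 69% power at 0.9 SD, against 81% for an outcome with a pre-treatment correlation of 0.5; 80% power needs an effect of about 1.02 SD. Adjusting for wave moves this to about 69% to 73% if wave explains 0 to 10% of the variance. CaGIC is no better: about 39% to 69% for an assumed 8 to 16 caregivers per group, before any wave adjustment. All these figures are approximate, because they apply a t-test to a rating scale and borrow the plan's general 0.9 SD.

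The SAP's covariate rule cannot be followed as written for PGIC, and it names the wrong visit for the AQ and Epps scenarios and, for most participants, for AIHQ and IRI. The stated power for the AQ and other outcomes with a pre-randomization score is not affected. This should be corrected, but it does not threaten the trial's main comparison.

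**What to change.** 1. **Sample Size Calculation.** Limit the claim of 16 per group, 0.9 SD and 80% power to outcomes with a pre-randomization score. Then add: *PGIC and CaGIC are first collected at T2 and have no pre-treatment value. For PGIC, 16 per group gives about 69% power at 0.9 SD (80% power at about 1.02 SD); this is approximate, because a t-test is applied to a rating scale, and it precedes any gain from adjusting for wave. CaGIC sensitivity is no better and depends on the number of caregivers.*

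2. **Statistical Analysis Plan, Primary Analyses.** Replace the T1 covariate and its exception with: *the pre-randomization value of the outcome (T0 or T1, as scheduled in Tables 1a and 1b), except for PGIC and CaGIC, which are first collected at T2 and have no pre-treatment value.*

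The cost is a few sentences in the sample size section and one phrase in the SAP. The stated sensitivity for these secondary outcomes becomes less favourable. No participants are added and no visit changes.

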* May be administered via phone, mail, REDCap survey, video conference call and/or in person; ** These measures will be collected at T1, if participants did not complete them at prior T0 due to protocol change.

Table 1 b. ICAN MEASURES AND TIMELINE Caregivers			
	T1	T2	T3
FrsBE*	X		
IRI PT and EC (perspective taking and empathy (Aim 1)*	X	X	WLC only
CaGIC Aggression & Empathy/ Perspective Taking*		X	WLC only

Intervention (Intervention to Change Attributions that are Negative; ICAN). In a group therapy format (approximately 5 subjects per group), ICAN will train perspective taking through role-playing and *perspective-positioning* exercises.

Each of the 6 sessions will include the core exercises outlined in Table 2. See publication for more detail.²¹

A) Role Play Video Scenario

Participants will watch video scenarios depicting situations in which a character's motives are ambiguous (e.g., some-one bumped into you). After watching the scenario, participants will be asked to generate possible motives. In other words, produce as many potential explanations for the behavior²² After generating possible motives, they will be asked to role-play the scenario assuming a positive interpretation of the motive for the observed behavior. After the role-play, participants will be asked questions to process the experience and how the role play changed how they felt about the person's actions.

B) Perspective-Positioning Personal Experiences

Participants will be asked to produce personal examples of situations in which someone's behaviors led to an unpleasant outcome for the participant, and possibly perceived by the participant as purposeful. After introducing this scenario to the group, the participant will take part in a Perspective-positioning exercise in which participants will sit in one chair representing self-perspective (Chair A) to explore his/ her own thoughts and feelings surrounding the situation, and then move to a different Chair (Chair B) to experience the other person's perspective, eliciting their thoughts and feelings. After the Perspective-positioning activity, participants will be asked questions to help them process the experience and how it felt to "be" the other person and what they learned about the other person's feelings and motives for their actions, and how that in turn changed how they felt about the situation and the person's actions.

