- Depression (inclusion): Severe Depression and/or perceived risk to self or others will be evaluated. If the participant is severely depressed or a perceived risk to self or others, the participant will be provided with Mental health resources, and if suicide risk, approved suicide protocol will be utilized. Additionally, this person will be excluded, and screening will discontinue.
- Negative attribution and perspective taking (inclusion): Participants will be presented with two different attribution measures (Epps scenarios or AIHQ) and a perspective taking measure (IRI respective taking). Since the intervention trains perspective taking for negative attribution styles, participants must have abnormal attribution or perspective taking scores on one of these measures.
- Other measures administered at the screening visit (not inclusion criteria), are indicated in Table 1 a (Screen T0) and include COWAT and Stroop Color word interference.

**Past screen failures and re-screening: Several new inclusion criteria have been added since the study start, and it is possible the changes may have altered the eligibility of earlier screened subjects. Subjects who initially failed screening will be allowed to be re-screened. Formerly excluded subjects will be contacted to see if they are interested in being screened again. If they are interested in being screened again, they will be re-consented (explaining they have previously been screened and failed and are now being re-tested) and re-administered all assessments as outlined in the protocol with the exception of subjects who have screen failed within 8 weeks from the new inclusion criteria.

Assessment Visits T1, T2, and T3. Assessments as outlined in Tables 1 a and b (except for the CSQ8 and the Post-Treatment Qualitative Interview; see below) will be conducted by the blinded RA. For T2, the RA will be blinded to group assignment. Because T3 is only WLCs, the RA will no longer be blinded to group assignment at that point. At the end of T2, the blinded RA will complete a survey on their belief regarding group allocation.

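### The T2 medication and therapy status update is left with the blinded RA and may lead participants to reveal their allocation

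*Combined protocol and SAP*

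**What the plan says.** Assessment Visits T1, T2, and T3 assigns the measures in Tables 1a and 1b as follows: they "will be conducted by the blinded RA", "except for the CSQ8 and the Post-Treatment Qualitative Interview; see below". The same section states "For T2, the RA will be blinded to group assignment" and adds a check: "At the end of T2, the blinded RA will complete a survey on their belief regarding group allocation".

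Table 1a collects "medication infor and therapy status" at T0, together with demographics and injury history. It then lists "Med and therapy status update only" at T1, at T2, and at T3 for WLC participants. The item is starred, and the footnote says that starred items "May be administered via phone, mail, REDCap survey, video conference call and/or in person".

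Under Satisfaction Survey (CSQ8), "an unblinded RA will be responsible for collecting data on the CSQ-8". The section gives two reasons: candid feedback and keeping the RAs blinded. The qualitative interview is handled in the same way for the same reasons. Under Randomization and Stratification, an unblinded RA also tells participants their allocation.

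**The concern.** The plan recognises that some T2 contacts could reveal the arm to the assessor, and it moves two of them to unblinded staff. The therapy status update was not moved. At T2 one arm has just completed a group therapy and the other has not started it. A participant who mentions that therapy when asked for an update tells the RA which arm they are in.

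What is at stake is assessor blinding for whatever that RA administers to that participant afterwards. At T2 this includes TASIT, Epps and AIHQ, and any questionnaire given by phone, video or in person. A secondary stake is what the allocation-belief survey can teach the planned larger trial. If blinding fails, a bare guess will not show whether the schedule caused it or something else did.

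**Working it through.** The plan gives no figure for this point, so the check sets its provisions side by side.

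1. **Who collects the item.** Assessment Visits T1, T2, and T3 gives the blinded RA everything in Tables 1a and 1b except two named items. The status update is marked at T2 in Table 1a and is not one of the two. Read as written, it belongs to the blinded RA.

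2. **What lies between the T1 and T2 updates.** Intervention Procedures and Treatment Fidelity describes six weekly sessions starting after T1 for ICAN participants, and postpones WLC treatment until T2 data are in. Procedures places T2 about 1 to 2 weeks after ICAN participants finish. The T1-to-T2 interval therefore contains the whole programme in one arm and none of it in the other.

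3. **Would a participant call it therapy?** The Intervention section describes ICAN as group therapy, and the qualitative interview uses the same term with participants. It would be natural to mention it in answer to a therapy question unless the question rules it out.

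4. **What would prevent disclosure.** The documents contain no wording that limits the item to outside treatment, no rule on its position within T2, and no request to participants to keep their allocation to themselves. Mail or REDCap is permitted for this item but not required, and the blinded RA is not barred from seeing the returned form.

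5. **What could be affected.**
   - The primary outcome (Aggression Questionnaire) and the secondary outcomes (PROMIS Anger, PGIC, CaGIC) are rated by the participant or caregiver. Several modes are allowed for these, including phone and in person.
   - Epps, AIHQ and TASIT carry no mode asterisk in Table 1a, so they are not among the items cleared for mail or REDCap.
   - The Epps and AIHQ attribution and anger scores are the participant's own ratings on a scale. The AIHQ open-ended answer on motive is scored afterwards by a pair of independent raters. The Epps open-ended answer is audio recorded, and the analysis plan names no analysis of it.
   - TASIT is not in the Table 1 outcome list, although its description says that its three subtests will be analysed.

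6. **How many participants.** From Sample Size Calculation: 20 per group randomized, with 20% dropout allowed. Expected completers per group = 20 × (1 − 0.20) = 16. The item therefore concerns 16 to 20 ICAN participants at T2.

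7. **Disclosure rate.** The documents give none. Let d be the share of ICAN participants who disclose, and assume that the RA otherwise guesses with even odds. The proportion of correct guesses in that arm is d + 0.5 × (1 − d):
   - d = 0: 0 + 0.5 × 1 = 50%
   - d = 0.5: 0.5 + 0.5 × 0.5 = 75%
   - d = 1: 1 + 0 = 100%

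   Nothing in the documents favours one value of d over another. The range shows only that the result could lie anywhere from chance to complete unblinding.

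**The case against.** Much of the opposing case is sound.

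- **Wording.** The question text is not given. The item begins at T0, before any study treatment, and fits the eligibility rules on stable medication and on current behavioral therapy for anger. It may be meant only for outside treatment. A question about current therapy would also miss ICAN, which has ended by T2. This stands, and it rules out a firmer claim that ICAN participants will answer by naming the programme. It does not close the gap: a question about therapy for anger could still draw a mention of ICAN unless study treatment is expressly excluded.
- **Order.** A reader might infer from the row order in Table 1a that the update opens the T2 visit and contaminates everything after it. Row order is not administration order, and Procedures allows visits to be split over several sessions. The order is simply unspecified.
- **Mode.** Mail or REDCap collection would need no conversation with the RA. This lowers the risk without removing it.
- **Comparison with the excepted items.** At T2 the CSQ-8 and interview go to ICAN participants only, so administering them reveals the arm by itself. The status update goes to both arms and reveals nothing unless the participant does. The comparison shows that the plan cares about this kind of leak, not that the items are equivalent.
- **Impact.** Most outcomes are self- or caregiver-rated, and participants know their arm in any waitlist design, so expectancy in self-report exists whatever the RA knows. This stands and keeps the point modest.
- **Allocation-belief survey.** A reader might infer that disclosure would invalidate it. It would not: a survey that picks up disclosure is doing its job. Its limits are that it comes at the end of T2, so it detects unblinding without preventing it, and that it is not described as recording the reason for the belief.
- **One-sidedness.** Only ICAN participants have sessions to report, but a WLC participant could reveal the arm by saying that they are still waiting.

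**Conclusion.** The concern holds in a limited form. As written, the assignment rule gives the blinded RA a T2 item that may elicit disclosure of allocation, and the plan has no safeguard for that item. This is an avoidable gap in protection that the plan itself adopted.

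The conclusion rests on reading the two exceptions as complete and on the possibility that participants count ICAN as therapy. It does not rest on any assumed disclosure rate. The documents do not support saying that disclosure will occur, that it comes before the outcome measures, that a given share of participants will disclose, or that the primary result is biased by a stated amount. The consequence is of unknown size, is limited for the self- and caregiver-rated outcomes, and is greatest for RA-administered measures. It justifies a small protocol clarification and has no bearing on the sample size or the ANCOVA.

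**What to change.** Choose one of two changes:

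- Add the T2 medication and therapy status update to the exceptions in Assessment Visits T1, T2, and T3, and have the existing unblinded RA collect it in both arms.
- Keep it with the blinded RA, but require that it be collected after all other T2 measures and the allocation-belief survey, including when T2 is split over several sessions.

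The first is somewhat safer. Waves are small (about 6 to 10 participants) and randomization is blocked, so an RA who learns some allocations late in each visit may guess others in the same wave more easily.

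With either option, word the item to exclude study therapy and remind participants before T2 not to mention their group. It would also help to have the RA note any disclosure during T2, so that the allocation-belief survey can be interpreted.

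The cost is a sentence or two in the protocol and, under the first option, a brief extra contact at T2. For ICAN participants it could be combined with the unblinded RA's CSQ-8 contact, so the added burden falls mainly on WLC participants. No endpoint, sample size or treatment changes.
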